4.2 Phase II: AVD-Brentuximab Vedotin Therapy

AVD dosing will be as described in Table 4-A, in conjunction with brentuximab vedotin at the MTD determined in the phase 1 portion of the study. The phase I MTD was determined to be 1.2 mg/kg. As in phase 1, drugs will be given on days 1 (+/- 2 days) and

15 (+/- 2 days) on a 28-day cycle for a total of 6 cycles. Brentuximab vedotin will be administered *after* AVD (doxorubicin 25 mg/m², vinblastine 6 mg/m², dacarbazine 375 mg/m²).

If treatment is delayed (<7 days if during cycle 1, or <2 weeks if occurring during subsequent cycles), once treatment is resumed the next dose will be scheduled two weeks after treatment is restarted.

4.3 Radiation Therapy

Involved field radiotherapy should be given at the discretion of the investigator after chemotherapy if there was bulky (> 10cm) disease at diagnosis as suggested in the NCCN guidelines. Radiation therapy initiation will be within 2 weeks after protocol therapy. Radiotherapy may be performed during the follow-up period according to institutional standards.

4.4 Supportive Therapy

4.4.1 Growth Factor

GCSF will be administered on Days 2-10 and 16-24 throughout each 28-day cycle using standard doses. Pegfilgrastim may be substituted for GCSF and be administered on days 2 and 16, either by clinical staff or via autoinjector applied on the day of protocol treatment.

4.4.2 HAART

HAART is a requirement for the duration of the study. Participants must be on HAART therapy for at least 7 days before therapy. The specific agents are at the discretion of the Investigator and use of agents currently available on an expanded access basis is allowed. Use of experimental antiretroviral agents or those containing zidovudine (including Combivir® and Trizivir®), ritonavir (including Kaletra®), Cobicistat (Stribild®), or another potent CYP3 inhibitor are prohibited. In order to be eligible, participants taking zidovudine- or ritonavir-based HAART must change to a different regimen 7 days prior to therapy initiation. Changes to HAART therapy may be made if medically necessary (toxicity, failure of regimen, etc.).

4.4.3 Pneumocystis prophylaxis

Trimethoprim sulfamethoxazole (Bactrim) must be given at the onset of therapy for Pneumocystis and Toxoplasmosis prophylaxis, according to current CDC guidelines which can be found here: https://aidsinfo.nih.gov/guidelines/html/4/adult-and-adolescent-opportunisticinfection/0

Alternatively, dapsone (50 mg PO twice daily), atovaquone, or aerosolized pentamidine may be substituted for Pneumocystis prophylaxis in participants allergic to sulfonamides. Pneumocystis prophylaxis will be continued once therapy has been discontinued.

4.4.4 Mycobacterium avium complex (MAC) prophylaxis

Azithromycin 1,200 mg PO once weekly must be initiated for prophylaxis if the

CD4 count falls below 50 cells/ μ L or is expected to drop below 50 cells/ μ l while on chemotherapy. Prophylaxis may be discontinued once the CD4 count is deemed reliably above 50 cells/ μ L by the treating investigator.

Due to the glycoprotein P inhibition properties of azithromycin, this may increase the chemotherapy drug exposure and contribute to increased toxicity. Sections 3.1.19, 7.3.7, and Appendix XIII state that P-glycoprotein inhibitors, including azithromycin, are disallowed medications on protocol. This limited exception is permitted in the case of MAC prophylaxis.

Based on the pharmacokinetics of azithromycin and brentuximab vedotin, the study team recommends giving the azithromycin on Days 5, 12, 19, and 26 of each cycle.

4.4.5 Pre-infusion prophylaxis

Pre-infusion prophylaxis (e.g., diphenhydramine) may be administered per institutional guidelines.

4.4.6 Quinolone antibacterial prophylaxis

For participants with a CD4+ T cell count of < 100/mm³ at baseline or whose CD4 count decreases below 100/mm³ during protocol therapy, antibiotic prophylaxis covering the nadir is recommended with quinolone or equivalent. Ciprofloxacin is not preferred due to being a moderate CYP3A4 inhibitor and caution should be exercised due to drug-drug interactions (See Appendix XIII).

4.5 Study Duration

Participants will receive brentuximab vedotin in conjunction with standard, fixed, doses of doxorubicin 25 mg/m², vinblastine 6 mg/m², and dacarbazine 375 mg/m² on days 1 and 15 of a 28-day cycle for 6 cycles. Participants will be followed for a total of 5 years, every 3 months for the first 2 years and every 6 months for years 3 to 5 of follow up.

Participants who discontinue all protocol therapy after having a CR or PR are followed for up to 5 years after treatment for recurrence and survival. Participants who discontinue protocol therapy due to disease progression or other reasons (Section 4.6) are followed for survival only for up to 5 years after treatment or until death, whichever occurs first. Participants who cross over to non-protocol therapy (if PR or stable disease at physician discretion), or other reasons will be followed for survival for up to 5 years after treatment. Participants removed from study for unacceptable adverse event(s) will be followed until resolution or stabilization of the adverse event.

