4.6 Criteria for Permanent Removal from Treatment

After enrollment, participants will be permanently withdrawn from study treatment for any of the following reasons. In the event of withdrawal from treatment, the reason for study treatment removal and the date the participant was removed must be documented in the Off Protocol Treatment Form in AdvantageEDCSM. See Section 8.4 on evaluations to be performed at early discontinuation of therapy.

4.6.1 Participants who experience a delay of over 7 days in cycle 1 will be removed from protocol therapy. For subsequent cycles, if two sequential doses of AVD + BV or AVD alone are held due to unresolved toxicity, leading to a treatment delay of an
additional 2 weeks (i.e., 4 weeks between doses), the participant will be taken off protocol therapy. The participant will be followed for survival and may resume AVD treatment off study.

- 4.6.2 Severe toxicities as outlined in Section 5.0.
- 4.6.3 Progressive lymphoma at any time while on study.
- 4.6.4 Voluntary withdrawal.
- 4.6.5 The investigator has the right to remove participants from study for clinical reasons which he or she believes to be life threatening or resulting in significant morbidity to the participant.
- 4.6.6 Any participant who develops HBV reactivation or acute Hepatitis B as defined by the reappearance of a previously suppressed hepatitis B surface antigen, a positive IgM hepatitis B core antibody, and a positive viral load. Any participant with Hepatitis B or C who has worsening liver function as defined by Section 5.2.5 will also be removed from study.
- 4.6.7 Participants who become pregnant or breast-feed.
- 4.6.8 Participants with progressive disease at the end of cycle 2 will be removed from study treatment, while participants with stable disease may be removed from the study treatment at the discretion of the local responsible investigator. Progressive or stable disease defined at cycle 2 will be based by CT criteria only, as FDG-PET has yet to be validated in HIV-associated HL.
- 4.6.9 If found by central pathology review to not have the diagnosis of HIV-HL.

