- 4.6.10 If the participant has had two cycles of AVD + brentuximab vedotin and develops recurrent Grade 3 peripheral neuropathy despite dose reductions of brentuximab vedotin and vinblastine, the participant may continue the study receiving AVD with dose adjustments in vinblastine as clinically necessary, keeping in mind to maintain the dose and schedule as in standard therapy, or may be removed from protocol treatment. This decision will be at the discretion of the investigator.

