The studies listed below will be performed post-therapy within 6-8 weeks of the last treatment dose (6-8 weeks after Cycle 6 Day 15; all follow up time points for post-treatment evaluations should be calculated in reference to this treatment discontinuation visit). Studies will then be repeated every 3 months (+/- 7 days) thereafter for 2 years; every 6 months (+/- 7 days) for the third through the fifth years unless otherwise specified. All study participants should be followed for up to 5 years after treatment discontinuation or until death if occurring before 5 years of treatment discontinuation. Participants who discontinue all protocol therapy after a CR or PR are followed for up to 5 years after treatment for recurrence and survival. Participants who discontinue protocol therapy due

to disease progression or other reasons are followed for survival for up to 5 years after treatment discontinuation. No additional studies except follow up for survival are required after disease progression. In those instances in which a third party payer denies payment for some or all of these laboratory analyses, absence of these test results will not be considered a protocol violation.

- 8.3.1 Medical history.
- 8.3.2 Physical examination, including performance status (see Appendix III, Performance Status Scale), vital signs (weight, height, body surface area), neurological examination, and if possible, two dimensional measurement of all palpable, peripheral lymph nodes and measurement of other sites of disease present on physical exam.
- 8.3.3 At the conclusion of chemotherapy, a full body FDG-PET/CT scan will be done between 6-8 weeks post the final treatment dose, Cycle 6 Day 15. This will be the final FDG-PET/CT needed for the study. A combined FDG-PET/CT or FDG-PET + CT scans with and without IV contrast are required for the post-treatment scan. If a participant has an allergy to IV contrast, a CT scan without contrast will be permitted. As the false positive rate of FDG-PET scans may be higher in the HIV population, a biopsy of an unexpected FDG-PET avid lesion is recommended but remains at the discretion of the investigator.
- 8.3.4 CT scan with oral/IV contrast every 6 months for 5 years. To begin 6 months from the post treatment FDG-PET/CT scan, obtained 6-8 weeks post the final chemotherapy dose (See Section 8.3.3).

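### Participants who stop therapy without progression and without a documented CR/PR go to survival follow-up only, and the primary 2-year PFS has no stated censoring rule, so a few progressions can be missed

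*Combined protocol and SAP*

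**What the plan says.** **Endpoint.** Section 11.2 (LYSARC 16.2) estimates 2-year PFS in 51 participants by Kaplan-Meier with Greenwood intervals. LYSARC 16.0 pools the French and US data.

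**Follow-up after stopping.** Section 4.5 gives recurrence follow-up to those who stop after CR or PR. Those who stop for progression or for other reasons listed in 4.6 "are followed for survival only for up to 5 years after treatment or until death, whichever occurs first". The same section adds: "Participants who cross over to non-protocol therapy (if PR or stable disease at physician discretion), or other reasons will be followed for survival". Section 4.6.1, on treatment delay, says: "The participant will be followed for survival and may resume AVD treatment off study".

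Section 8.3 repeats the responder rule, "Participants who discontinue all protocol therapy after a CR or PR are followed for up to 5 years after treatment for recurrence and survival", and then says that those who stop due "to disease progression or other reasons are followed for survival for up to 5 years". It also says: "No additional studies except follow up for survival are required after disease progression". Section 8.4.1 puts early discontinuers on survival follow-up only, and its visit consists of history, examination and blood tests. The early-discontinuation column of Appendix I has no PET or CT. The LYSARC synopsis, 9.5, 9.6 and 13.1 carry the same rules.

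**PFS definition.** The events (progression or death) appear only in the PET predictive-value text of 11.4 (LYSARC 16.4). Section 9.2 gives a time origin for time to progression, not for PFS.

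**The concern.** A PFS estimate needs progression to be looked for until it happens. Section 4.6 lists several reasons for stopping that are not progression, among them toxicity delay, investigator decision, hepatitis, pregnancy and stable disease at cycle 2. The first response scan is at days 22-28 of cycle 2 (8.2.3), so a participant removed for a delay in cycle 1 cannot have a scan-documented response and falls into the survival-only group. Deaths in that group are still captured; non-fatal progressions are not.

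With no censoring rule, the analyst must choose. Censoring at stopping assumes that stoppers have the same prognosis as those who continue. Leaving them at risk until death treats an unseen progression as no event. Neither choice pushes the estimate down unless stoppers do better than the others, and progressions that were never assessed cannot be recovered at analysis. Because the sections disagree about responders, sites may also follow similar participants differently.

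**Working it through.** **1. The plan's own figure.** With p = 0.85 and a target half-width of 0.10, n = 1.96² × 0.85 × 0.15 / 0.10² = 49.0; with z = 2 it is 51.0. At n = 51 the half-width is 1.96 × √(0.85 × 0.15 / 51) = 9.8 points. The stated size reproduces.

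**2. The sections side by side.**

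| Who stops | 4.5 | 4.6.1 | 8.3 | 8.4.1 |
|---|---|---|---|---|
| After CR/PR | Recurrence and survival; but PR with crossover: survival | Survival, no responder exception | Recurrence and survival | Survival only, no exception stated, though responders are not among its examples |
| No progression, no CR/PR | Survival only | Survival | Survival | Survival only |

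The second row is consistent throughout: no progression assessment. The first row is not. The 8.3 sentence that waives studies after progression suggests that they continue before it, but the same paragraph sends other reasons to survival follow-up.

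**3. How many are affected.** The documents give no stopping rate for this trial. I assume 10 to 19% stop, uniformly over months 1 to 5. The 19% is 6/31 from the phase 1 cohort cited in 2.4.2. One quarter then stop before month 2, with no response scan. Of the other three quarters, I assume 80 to 90% are responders. The share affected is 0.25 + 0.75 × (0.10 to 0.20) = 0.325 to 0.40. Applied to 51 × 0.10 = 5.1 and 51 × 0.19 = 9.7 stoppers, that is 1.7 to 3.9, or about 2 to 4 participants.

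**4. Censored at stopping.** If k such participants have true 2-year PFS q and the overall value is 85%, Kaplan-Meier estimates roughly (51 × 0.85 − kq) / (51 − k).
- k = 2, q = 0.65: 42.05/49 = 0.858, or +0.8 points.
- k = 4, q = 0.65: 40.75/47 = 0.867, or +1.7.
- q = 0.85: 0 for any k.

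This slightly overstates the bias, because participants contribute time before they stop. A simulation (200,000 trials of 51 per scenario, exponential PFS, 30% of PFS events assumed to be deaths) allows for that. Bias in points, censored at stopping / at risk until death:

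| Stopping rate, responder share | Stopper PFS 65% | 75% | 85% (equal risk) |
|---|---|---|---|
| 10%, 90% | +0.61 / +0.72 | +0.31 / +0.52 | 0 / +0.31 |
| 10%, 80% | +0.75 / +0.87 | +0.37 / +0.63 | 0 / +0.38 |
| 19%, 90% | +1.20 / +1.37 | +0.60 / +0.98 | 0 / +0.60 |
| 19%, 80% | +1.47 / +1.65 | +0.75 / +1.20 | 0 / +0.72 |
| 10%, no CR/PR exception | +1.90 / +2.08 | +0.95 / +1.50 | 0 / +0.91 |
| 19%, no CR/PR exception | +4.00 / +3.96 | +2.02 / +2.86 | 0 / +1.73 |

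**5. At risk until death.** The second figure in each cell is simply missed progressions divided by 51. At stopper PFS 65% with the exception, 0.37/51 = 0.7 points and 0.84/51 = 1.6 (1.65 before rounding of the count). These are maxima: a death within 24 months after an unseen progression would still count as an event. An assumed mean post-progression survival of 24 months reduces them by about a third.

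**6. Precision.** At equal risk, the average Greenwood half-width under censoring is 9.7 to 9.9 points with the exception (9.6 if fully observed), and 10.0 or 10.5 without it.

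**The case against.** The best defence is that the effect is small and rests on assumptions. Stopping rate, stopper prognosis, responder share and death share are not given for this trial. The 6/31 proxy comes from a cohort in which 25 of 31 received ABVD. Section 2.3 implies a similar 18% for ABVD in HIV-associated disease (82% tolerated six courses), but that is a different regimen too. Under 4.6.10, "the participant may continue the study receiving AVD with dose adjustments in vinblastine as clinically necessary", so stopping brentuximab vedotin alone need not end study follow-up. Phase II is single-arm estimation with no efficacy threshold, so no decision turns on about 1 point. All of this stands, and it limits the size.

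It does not remove the gap. Following the text as written leaves progression unassessed in the primary endpoint.

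Three stronger inferences are tempting and are not supported.
- *That the estimate is inflated by about 4 points.* That needs 8.4.1 to override the explicit CR/PR sentences in 4.5 and 8.3, together with 19% stopping and stopper PFS of 65%. The more specific text favours the smaller effect.
- *That 51 is the wrong sample size.* Step 6 shows it is not affected.
- *That PFS is wholly undefined.* Section 11.4 implies the events and Section 11.2 names the estimator. What is missing is an explicit definition with time origin, censoring date and handling of new therapy.

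**Conclusion.** The concern holds as a cheap improvement. Both protocols assign survival follow-up without imaging to participants who stop without progression and without a documented CR/PR, contradict themselves on responders, and state no censoring rule for the primary PFS.

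With the CR/PR exception honoured, about 2 to 4 of 51 are affected. Censoring at stopping gives no bias if stoppers have the same risk as the others, and about +0.3 to +1.5 points if their 2-year PFS is 65 to 75%. Keeping them at risk until death gives at most about +0.3 to +1.7. All of these are well inside the planned half-width of 9.8. That stoppers do worse is plausible but assumed. The finding qualifies how the primary estimate is read; it does not undermine it.

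**What to change.** - Reconcile 4.5, 4.6.1, 8.3, 8.4.1 and Appendix I, and the LYSARC synopsis, 9.5, 9.6, 13.1 and flow chart. Consenting participants with confirmed disease who stop without documented progression should stay on the existing follow-up visits and 6-monthly CT until progression. Survival-only follow-up after documented progression can stay. Cases removed under 4.6.9 ("If found by central pathology review to not have the diagnosis of HIV-HL") are outside this proposal.
- State an anchor date for early stoppers, for example the last dose. The present CT series is timed from the scan taken 6-8 weeks after Cycle 6 Day 15, which they do not have.
- Where a scan is not appropriate or not obtained, including for those who stopped before the amendment, record progression status and date from routine care.
- Record the date of any new anti-lymphoma therapy.
- In 11.2 and LYSARC 16.2, define PFS as time from first dose to progression or death, censored at the last progression assessment, with a stated handling of therapy started before progression. A sensitivity analysis counting participants lost to progression assessment as events, labelled a lower bound, is optional.

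**Cost.** Amendment of two protocols with their approvals, one added data field, and CTs of a type already scheduled for about 2 to 4 participants (up to about 9 if 8.4.1 has been applied to everyone). No new participants or procedure types. The PFS definition and censoring rule need only text.

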4.6 Criteria for Permanent Removal from Treatment

After enrollment, participants will be permanently withdrawn from study treatment for any of the following reasons. In the event of withdrawal from treatment, the reason for study treatment removal and the date the participant was removed must be documented in the Off Protocol Treatment Form in AdvantageEDCSM. See Section 8.4 on evaluations to be performed at early discontinuation of therapy.

4.6.1 Participants who experience a delay of over 7 days in cycle 1 will be removed from protocol therapy. For subsequent cycles, if two sequential doses of AVD + BV or AVD alone are held due to unresolved toxicity, leading to a treatment delay of an
additional 2 weeks (i.e., 4 weeks between doses), the participant will be taken off protocol therapy. The participant will be followed for survival and may resume AVD treatment off study.

- 4.6.2 Severe toxicities as outlined in Section 5.0.
- 4.6.3 Progressive lymphoma at any time while on study.
- 4.6.4 Voluntary withdrawal.
- 4.6.5 The investigator has the right to remove participants from study for clinical reasons which he or she believes to be life threatening or resulting in significant morbidity to the participant.
- 4.6.6 Any participant who develops HBV reactivation or acute Hepatitis B as defined by the reappearance of a previously suppressed hepatitis B surface antigen, a positive IgM hepatitis B core antibody, and a positive viral load. Any participant with Hepatitis B or C who has worsening liver function as defined by Section 5.2.5 will also be removed from study.
- 4.6.7 Participants who become pregnant or breast-feed.
- 4.6.8 Participants with progressive disease at the end of cycle 2 will be removed from study treatment, while participants with stable disease may be removed from the study treatment at the discretion of the local responsible investigator. Progressive or stable disease defined at cycle 2 will be based by CT criteria only, as FDG-PET has yet to be validated in HIV-associated HL.
- 4.6.9 If found by central pathology review to not have the diagnosis of HIV-HL.
- 4.6.10 If the participant has had two cycles of AVD + brentuximab vedotin and develops recurrent Grade 3 peripheral neuropathy despite dose reductions of brentuximab vedotin and vinblastine, the participant may continue the study receiving AVD with dose adjustments in vinblastine as clinically necessary, keeping in mind to maintain the dose and schedule as in standard therapy, or may be removed from protocol treatment. This decision will be at the discretion of the investigator.

4.7 Criteria for Early Study Termination

- 4.7.1 An early stopping rule will be established such that the trial will be terminated if either or both of the following conditions hold:
 - 1. If the highest dose, the 1.2mg/kg dose, moves forward into the phase II portion of the study, and if more than 10% of the participants experience a grade 3 motor or sensory neurotoxicity lasting for more than 4 weeks, the trial will be terminated. The first 10 participants in the phase II portion of the study at the 1.2 mg/kg dose will be monitored for this outcome. If more than 3 out of the 10 participants experience grade 3 neurotoxicity, this will be considered sufficient to stop the trial. With an underlying probability of grade 3 neuropathy of no more than 10%, the probability of observing > 3 participants with grade 3 neuropathy is less than 5%.
 - 2. If any PML case is diagnosed when the CD4 count is above 50, the trial will be terminated.

4.7.2 Request by the protocol chairs, AMC, IRB, NCI, OHRP, or pharmaceutical sponsors.

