A phase 2 study of brentuximab vedotin (SGN-35) studied 102 patients with relapsed or refractory HL post autologous stem cell transplant⁴¹. Patients received brentuximab vedotin every three weeks at a dose of 1.8 mg/kg. The median duration of brentuximab vedotin treatment was 27 weeks (range 3-54). The most common treatment-related adverse events (AEs) of any grade in >15% of patients were peripheral sensory neuropathy (43%), fatigue (40%), nausea (35%), neutropenia (19%), diarrhea (18%), and pyrexia (16%). Most events were Grade 1 or 2. The Grade 3 treatment-related AEs reported in more than 1 patient were neutropenia (14%), peripheral sensory neuropathy (5%), thrombocytopenia and hyperglycemia (3% each), and fatigue (2%). The only Grade 4 treatment-related events were neutropenia (4%), and thrombocytopenia, abdominal pain, and pulmonary embolism (1% each). There we no related Grade 5 events. Eighteen patients discontinued treatment due to an adverse event⁴¹. While no interim analysis was presented with respect to overall response rate, there was a 95% reduction of tumor size and an 83% resolution of B symptoms⁴¹.

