The AMC ODMC provides listings of all reported adverse events and serious adverse events to the Protocol Chair and Co-chair(s) for review on a regular basis. The AMC ODMC compiles these events in a tabular format and posts them on the password-protected section of the AMC web site where these reports are updated nightly. The AMC web site is accessible to all AMC investigators, co-investigators, and their staff. Email notification that this information is available on the web site will be sent to all site PIs. It is the responsibility of each site to provide this information to their respective IRBs, if required by their IRB. For blinded studies, the serious adverse events are reviewed and tabulated without treatment assignment. The AMC Medical Monitor will review listings of all reported adverse events on a quarterly basis for safety concerns.

Accrual summaries for each AMC trial are updated nightly on the password-protected section of the AMC web site. The progress of each AMC trial is reviewed regularly by the Protocol Chair and also by the appropriate disease-oriented Working Group during scheduled conference calls. For phase I dose escalation trials, dose escalation (or dose de-escalation) is based on the rules in the protocol and the Protocol Chair, AMC Medical Monitor, and Group Statistician determine whether these criteria have been met. For phase II trials, stopping the trial for toxicity or efficacy, or suspending enrollment pending observation of responses in a multi-stage phase II trial, is based on meeting criteria stated in the protocol, and the Protocol Chair, AMC Medical Monitor, and Group Statistician determine whether these criteria have been met.

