13.4 Premature discontinuation of the study

The sponsor reserves the right to stop the trial at any time. The investigators will be informed of this decision in writing.

The same applies to any investigator wanting to discontinue his/her participation to the trial. The investigator must immediately inform the sponsor in writing of this decision.

An early stopping rule will be established such that the trial will be terminated if either or both of the following conditions hold:

- 1. If more than 10% of the subjects experience a grade 3 motor or sensory neurotoxicity lasting for more than 4 weeks, the trial will be terminated. The first 10 patients in the phase II portion of the study at the 1.2 mg/kg dose will be monitored for this outcome. If more than 3 out of the first 10 patients in the phase II study experience grade 3 neurotoxicity, this will be considered sufficient to stop the trial. With an underlying probability of grade 3 neuropathy of no more than 10%, the probability of observing > 3 patients with grade 3 neuropathy is less than 5%.
- 2. If any PML case is diagnosed when the CD4 count is above 50, the trial will be terminated.

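### The neurotoxicity stopping rule states two thresholds without saying which governs, and the printed false-stop probability fits only one of them

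*Combined protocol and SAP*

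**What the plan says.** Item 1 of Section 4.7.1 in the AMC protocol applies once the 1.2 mg/kg dose has gone forward to phase II, which it has. It has four parts.

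1. The trial is to be terminated "if more than 10% of the participants experience a grade 3 motor or sensory neurotoxicity lasting for more than 4 weeks". No denominator or time of assessment is given.
2. A monitored set: "The first 10 participants in the phase II portion of the study at the 1.2 mg/kg dose will be monitored for this outcome".
3. A count: "If more than 3 out of the 10 participants experience grade 3 neurotoxicity, this will be considered sufficient to stop the trial". The 4-week duration is not restated.
4. An error statement: "With an underlying probability of grade 3 neuropathy of no more than 10%, the probability of observing > 3 participants with grade 3 neuropathy" is said to be below 5%.

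Section 13.4 of the LYSARC protocol repeats the structure and the same probability. Its two triggers read "If more than 10% of the subjects experience a grade 3 motor or sensory neurotoxicity lasting for more than 4 weeks" and "If more than 3 out of the first 10 patients in the phase II study experience grade 3 neurotoxicity".

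The statistical chapters (AMC Section 11, LYSARC Section 16) do not mention the rule. On stopping a phase II trial for toxicity, Appendix VII has this wording: "based on meeting criteria stated in the protocol, and the Protocol Chair, AMC Medical Monitor, and Group Statistician determine whether these criteria" (that is, whether they are satisfied).

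**The concern.** The first part is a complete and mandatory trigger. The third part is another trigger at a different level, and it is described only as sufficient. If the 10% is read on the 10 monitored participants, as the second part suggests, then 2 or 3 persistent events (20% or 30%) oblige the trial to stop under the first part. The third part is not met at those counts and does not say what to do.

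Appendix VII makes the written criteria decisive, so the chair, the medical monitor and the statistician could read the same text at 2 or 3 events and properly disagree. Following the first part literally gives up the false-stop protection that the protocol advertises. Following the third part alone leaves a termination instruction unmet. It is also unclear whether a grade 3 event that resolves within 4 weeks counts towards the 3 of 10.

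**Working it through.** **Inputs.** From Section 4.7.1: n = 10; the count boundary of more than 3, i.e. X ≥ 4; the share boundary of more than 10%; the reference true rate p = 0.10. From Section 11.2: phase II size 51. From Section 2.4.1: grade 3 sensory neuropathy in 5% of patients in the phase 2 single-agent study. That study used 1.8 mg/kg every 3 weeks and counted any duration, so 5% is only indicative here. True rates of 20% and 30% are my assumptions, because the documents name no unacceptable rate.

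**Formula.** P(X ≥ r) = Σ from k = r to n of C(n,k) p^k (1 − p)^(n − k). Every counted participant is taken to be fully evaluable.

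**The plan's own figure.** With n = 10 and p = 0.10, the probabilities of 0, 1, 2 and 3 events are 0.3487, 0.3874, 0.1937 and 0.0574.

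P(X ≥ 4) = 1 − 0.9872 = 0.0128. The printed bound of 5% is therefore correct for more than 3 of 10. It would not hold for 3 or more of 10, where the value is 0.0702.

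**The share trigger on the same 10.** More than 10% of 10 means X ≥ 2.

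P(X ≥ 2) = 1 − 0.3487 − 0.3874 = 0.2639, about five times the printed 5% (0.2639 / 0.05 = 5.3).

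**The zone where the two triggers part.** P(X = 2 or 3) = 0.1937 + 0.0574 = 0.2511. This takes both triggers to count the same persistent events.

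**The share trigger at full size.** 10% of 51 is 5.1, so more than 10% means X ≥ 6. One look at 51 gives 0.4024 at p = 0.10.

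| True rate | More than 3 of 10 | More than 10% at n = 10 | Exactly 2 or 3 of 10 | More than 10%, one look at n = 51 |
|---|---|---|---|---|
| 5% | 0.1% | 8.6% | 8.5% | 4.1% |
| 10% | 1.3% | 26.4% | 25.1% | 40.2% |
| 20% | 12.1% | 62.4% | 50.3% | 95.8% |
| 30% | 35.0% | 85.1% | 50.0% | not computed |

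If the share were checked after each participant from the 10th to the 51st, the stopping probability would be 30.8%, 74.4% and 99.1% at true rates of 5%, 10% and 20%. The documents schedule no looks for the share trigger, so its n = 10, n = 51 and sequential versions are all readings I have supplied.

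**The case against.** The best defence is that the item is one rule told in sequence: 10% is the tolerable true rate, the first 10 participants are the monitored set, more than 3 of 10 is the operating boundary, and the last sentence gives its error rate. That last sentence does use 10% as an underlying probability. There is also no strict contradiction. More than 3 of 10 always exceeds 10% of those 10, and the count is called sufficient, not necessary. This may well be the intention, but the text does not say so. The opening sentence is worded as a termination condition, and calling the count sufficient leaves that condition in force.

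A second objection is that the comparison uses one true rate for two event definitions. If the 10% in the error statement covers grade 3 events of any duration, the persistent rate is lower. If half of them persisted (an assumption), the share trigger would stop falsely with probability 8.6% at n = 10 and 4.1% at n = 51. This point stands as a limit on the size: 26% applies when the persistent event itself has a true rate of 10%. It also shows why the event definition has to be settled.

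Third, other protection exists. There are participant-level neuropathy rules (Section 4.6.10, Table 5-A), a neurotoxicity questionnaire each cycle (Section 8.2.4), routine adverse event review and the LYSARC data monitoring committee. Discretionary stopping is available under Section 4.7.2 and LYSARC Section 13.4. This limits the harm, but none of it tells anyone whether the mandatory criterion has been met.

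Finally, the review of the first 10 may already have taken place. Section 10.3 refers to data from treated participants, and the LYSARC version is dated April 2019 against a planned last inclusion in June 2017. The documents do not settle this. If that review is past, it still matters whether the share trigger continues to apply to later participants.

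**Conclusion.** The concern holds. Both protocols carry two triggers for the same toxicity, with different thresholds, no stated denominator for one and no stated duration for the other. Nothing says which governs. The printed bound of 5% is correct for more than 3 of 10 (1.3%) and does not describe the more-than-10% trigger. At a true persistent-event rate of 10%, that trigger gives 26% on the first 10 and 40% at a single look at 51. The chance of falling where only the share trigger is met is 25% at that rate, and about 50% at an assumed 20% or 30%.

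These figures rest on full evaluability, on the looks described, and on both triggers counting the same event. The consequences are limited to how this safety rule is applied; the primary estimate of two-year progression-free survival is not affected. It should be fixed because a mandatory stopping criterion needs a single reading.

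**What to change.** Reconcile AMC Section 4.7.1 item 1 and LYSARC Section 13.4 into one operating rule. State one threshold, one denominator and one event definition, say whether the 4-week duration is part of that definition, and print the false-stop probability that belongs to that rule. Which boundary applies is for the sponsor to decide.

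- If more than 3 of the first 10 is the intended boundary, reword the opening sentence so that 10% is the reference true rate and not a second trigger. The printed bound of 5% can then stay.
- If another boundary is intended, recompute the probability. Any boundary below more than 3 of 10 breaks the printed bound, since 3 or more of 10 already gives 7.0% at a true rate of 10%.

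It would also help, though it is optional, to say whether the rule continues beyond the first 10 and to print stopping probabilities at higher true rates.

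The cost is amendment wording in two sections and at most one recomputed number, with no new data or visits.
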